externally powered stepping for over ground walking and climbing stairs. Most importantly, the assistance provided by wearable robotic exoskeletons may reduce energy expenditure during walking and allow persons with MS to recover some degree of independent walking that is more efficient. Needless to say, this can have a profound impact on quality of life. Therefore, the purpose of this pilot study is to investigate whether using exoskeleton could promote recovery of walking in persons with MS. We hypothesize that participants will be able to walk with exoskeleton and with minimal to moderate trainer assistance after training (Aim1). We also plan to determine and compare physical and cognitive demands during over ground walking with and without exoskeleton (Aim2). We hypothesize that physical and cognitive demands will reduce (i.e. decrease oxygen cost and shorter reaction time) during over ground walking with exoskeleton and especially after training. The reduced physical and cognitive demands will promote energy conservation and prevent/delay fatigue in over ground walking in this population. *The innovation of this study is this wearable exoskeleton provides a unique opportunity not only to assist a sustained upright posture but also facilitate walking with better energy efficiency in individuals with MS. Overall, we expect these findings to support that exoskeleton will demonstrate greater efficacy to facilitate walking and can be applied extensively to improve quality of life in MS.*

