## Objectives

The purpose of this pilot study is to investigate whether using exoskeleton could promote recovery of walking in persons with MS. We hypothesize that participants will be able to walk with exoskeleton and with minimal to moderate trainer assistance after training (Aim1). We also plan to determine and compare physical and cognitive demands during over ground walking with and without exoskeleton (Aim2). We hypothesize that physical and cognitive demands will reduce (i.e. decrease oxygen cost and shorter reaction time) during over ground walking with exoskeleton and especially after training. The reduced physical and cognitive demands will promote energy conservation and prevent/delay fatigue in overground walking in this population. The wearable exoskeleton will be used in this study is Ekso®, by Ekso Bionics, formerly known as eLEGS®.

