7. Berg Balance Scale: A 14-item objective measure designed to assess static balance and fall risk in adult populations, with maximum summed score of 56 (higher scores represent better functional outcome). This task will be formed without using exoskeleton at pre-assessment and post-assessment.
8. Timed Up and Go Test: this task involves subject to stand from the standard chair, walk straight for 3 meters, turn around, walk back to the chair and sit down with shoes and assistive devices if any. A standard chair with arm rests will be place at the start of the testing course. A mark will be placed on the floor at the 3 meter distance. Subject will be asked to perform the task as fast as possible without losing their balance. One research member will stand next to the subject to monitor the subject performance to prevent falls. The time to complete the task will be measured and recorded. Subjects will also have recording of electromyography in the lower limbs i.e., sensors will be placed on the skin of the legs and thighs (4 on each leg) to non-invasively record muscle activity during walking. Additional sensors i.e., goniometers will be placed on the skin to non-invasively record joint angles of the hip, knee and ankle on each leg. These will be attached to the skin using hypoallergenic tape. This task will be formed without using exoskeleton at pre-assessment and with and without exoskeleton at post-assessment.

9. 6-minute walk test: Subjects will be asked to walk back and forth in a hallway with or without assistive device (consistent among assessment visits) for 6 minutes. The objective is to cover as much space as possible in 6 minutes. Subjects can slow down or stop to rest if they feel like, but should start walking when they feel they are able. Electromyography sensors will also be placed on the skin of the leg and trunk muscles to measure muscle activity. A research team member will walk behind the subject to prevent loss of balance during the test. This task will be formed without using exoskeleton at pre-assessment and with and without exoskeleton at post-assessment. In this tasks, we will measure physical demands and cognitive demand in separate trials or sessions:

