  - A. Physical demands measures: Physical demands during walking with and without EKSO will be determined by oxygen cost. Oxygen cost will be calculated from oxygen consumption as the product of gait speed and body weight [10]. Oxygen consumption will be collected on a breath-by-breath basis measured by a portable metabolic system (K4 b2 Cosmed). Prior to the testing, the system will be calibrated using room air and reference gas mixture [11]. During the testing, the subject will wear a face mask and a heart rate monitor at all times and will be asked to breathe normally. The portable device will be carried by the subject at where it will not interfere with the walking (i.e. upper back or waist).
  - B. Cognitive demands measure: Cognitive demands during walking with and without exoskeleton will be determined by reaction time using a dual-task paradigm [12]. Dual-task paradigm is commonly used to quantify the cognitive (i.e. attentional) resources allocated during a motor task such as walking and usually entails reciting the alphabet or counting backwards [13]. However, this specific measurement is limited by structural issues involving respiration, vocal responses or motor action of the upper limb (push a button) for which there are shared execution pathways with locomotion [14, 15] could interfere with the primary motor task, despite not being caused by competing demands for limited attentional resources. Thus, we chose a simple reaction task (RT), in which the response will be biting on a pressure sensor to make the response pathways as independent as possible from the motor pathways of locomotion [12]. Subjects will with and without EKSO (use same assistive device) at their preferred speed. The secondary RT task consists of biting a pressure transducer placed in the mouth in response to an unpredictable sensory (will not cause pain) electrical stimulation applied by an electrode on the back of the neck [12] without changing walking speed and pattern. The stimulation intensity will be adjusted for each individual before data collection. Shorter RT indicates that reduced amount of attentional resources are required.

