10. Timed 25 Feet Walk Test (T25-FW): this task will ask the subject to walk for 25 feet at comfortable pace. Subjects will wear their exercise or walking shoes and are allowed to use assistive device such as cane or walker if necessary. The start and finish line of the 25 feet test course will be marked with tape on the floor. Additional 5 feet at the end of start and finish will be used for subject to turn around. A chair will be provided next to the start area so the subject may rest. During the test, the subject will walk at his/her comfortable pace without losing balance followed by walking at maximal pace. Resting periods will be provided between trials. One trial for each pace will be performed. Trial will be repeated if subject cannot finish the task due to fatigue or loss of balance. A research team member will walk next to the subject for safety. The time to complete the tasks will be recorded. We will place markers on the skin of the legs and trunk and the marker data will be recorded by motion capture system. Electromyography sensors will also be placed on the skin of the leg and trunk muscles to measure muscle activity. This task will be formed without using exoskeleton at pre-assessment and with and without exoskeleton at post-assessment. A research team member will walk behind the subject to prevent loss of balance during the test. This task will be formed without using exoskeleton at pre-assessment and with and without exoskeleton at post-assessment. In this tasks, we will measure physical demands and cognitive demand in separate trials:
  - A. Physical demands measures: Physical demands during walking with and without EKSO will be determined by oxygen cost. Oxygen cost will be calculated from oxygen consumption as the product of gait speed and body weight [10]. Oxygen consumption will be collected on a breath-by-breath basis

measured by a portable metabolic system (K4 b2 Cosmed). Prior to the testing, the system will be calibrated using room air and reference gas mixture [11]. During the testing, the subject will wear a face mask and a heart rate monitor at all times and will be asked to breathe normally. The portable device will be carried by the subject at where it will not interfere with the walking (i.e. upper back or waist).

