#### Statistics

Descriptive analyses will be used for Aim 1. For Aim 2, outcome measures will be analyzed using separate paired t-test (exoskeleton vs. no-exoskeleton walking). We also plan to plot the trend at pre-and post- training for all outcome measures for each subject (without exoskeleton). Significant level will be set at .05.

This is a pilot study therefore no data is available to calculate sample size. The reason to enroll 15 subjects is based on the limited funds awarded to this project. We anticipate that the data from this study will allow for performance of power analysis to determine effect size and sample size for future studies.

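### Oxygen cost, the only physical-demand measure in Aim 2, is defined as a product with gait speed instead of a quotient; as written it can reverse the exoskeleton comparison

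*Combined protocol and SAP*

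**What the plan says.** Outcome Measures, item 9A (6-minute walk test), makes oxygen cost the measure of physical demand: "Physical demands during walking with and without EKSO will be determined by oxygen cost". It then defines it: "Oxygen cost will be calculated from oxygen consumption as the product of gait speed and body weight [10". Item 10A (Timed 25 Feet Walk Test) carries the same sentence. Neither item gives a formula or units, and the Statistics section neither restates nor corrects the definition.

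The Objectives fix the favourable direction: "physical and cognitive demands will reduce (i.e. decrease oxygen cost and shorter reaction time) during over ground walking with exoskeleton". Background Information names what is to be shown, that the device will "facilitate walking with better energy efficiency in individuals with MS". For Aim 2 the Statistics section says that "outcome measures will be analyzed using separate paired t-test (exoskeleton vs. no-exoskeleton walking"), at a significance level of .05.

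Gait speed is left free in both tests. In the 6-minute test, "The objective is to cover as much space as possible in 6 minutes", and participants may slow down or rest. In the 25-foot test, "the subject will walk at his/her comfortable pace without losing balance followed by walking at maximal pace".

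**The concern.** Energy efficiency of walking means oxygen used per unit of distance, scaled for body weight. Speed and weight then belong in the denominator. The printed sentence has no denominator and allows two literal readings:

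- **(a)** oxygen cost = speed × weight, which contains no oxygen data;
- **(b)** oxygen cost = oxygen consumption × speed × weight.

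Under either one, walking more slowly at the same oxygen consumption lowers the score, and the Objectives count a lower score as success. Per metre walked, the same change is a loss of efficiency.

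The physical-demand half of Aim 2 rests on this one variable. The Statistics section also says the data will feed power analysis and sample size for later studies, so an effect with the wrong sign would be carried forward. Aim 1 and the reaction-time half of Aim 2 are not affected.

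**Working it through.** The documents state no oxygen-cost figure, so there is nothing to reproduce. The question is when the printed definition and the per-distance quotient point in opposite directions.

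**Inputs.** The documents give no speeds and no oxygen consumption values, so both are assumed, as ratios of exoskeleton to no exoskeleton within one participant:

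- s = ratio of gait speeds
- v = ratio of oxygen consumption

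Body weight cancels if the same weight is used in both conditions.

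**Formulas** (ratio above 1 = higher score with the exoskeleton):

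- quotient, consumption / (speed × weight): v / s
- reading (a), speed × weight: s
- reading (b), consumption × speed × weight: v × s

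**When the direction reverses**

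- s < 1 (slower in the device): (a) reverses when v > s; (b) reverses when s < v < 1/s.
- s > 1 (faster in the device): (a) reverses when v < s; (b) reverses when 1/s < v < s.
- s = 1: neither reverses. Reading (b) gives the same ratio as the quotient, and (a) shows no change.

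For (b), the reversing range of v is 0.5 to 2.00 at s = 0.5, 0.7 to 1.43 at s = 0.7, and 0.9 to 1.11 at s = 0.9.

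**Examples**

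| s | v | Quotient v/s | (a) s | (b) v×s | (b) reversed? |
|---|---|---|---|---|---|
| 0.7 | 1.0 | 1.43 | 0.70 | 0.70 | yes |
| 0.7 | 1.2 | 1.71 | 0.70 | 0.84 | yes |
| 0.9 | 0.8 | 0.89 | 0.90 | 0.72 | no |
| 0.9 | 1.2 | 1.33 | 0.90 | 1.08 | no |
| 1.5 | 1.2 | 0.80 | 1.50 | 1.80 | yes |

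**In units.** Assume 75 kg, 800 mL/min in both conditions, 36 m/min without the device and 0.7 × 36 = 25.2 m/min with it.

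- Quotient: 800 / (36 × 75) = 0.296 and 800 / (25.2 × 75) = 0.423 mL/kg/m, ratio 1.43.
- Reading (b): 800 × 36 × 75 = 2,160,000 and 800 × 25.2 × 75 = 1,512,000, ratio 0.70.
- Reading (a): 36 × 75 = 2,700 and 25.2 × 75 = 1,890, ratio 0.70.

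**Grid.** Take v = 0.7 to 1.3 in steps of 0.1 (7 values per row); a ratio of exactly 1 is not counted as reversed.

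| s | (b) reversed, of 7 | (a) reversed, of 7 |
|---|---|---|
| 0.5 | 7 | 7 |
| 0.6 | 7 | 7 |
| 0.7 | 6 | 6 |
| 0.8 | 4 | 5 |
| 0.9 | 2 | 4 |
| 1.0 | 0 | 0 |
| 1.1 | 1 | 4 |
| 1.2 | 3 | 5 |

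Over s = 0.5 to 0.9 the totals are 26 of 35 for (b) and 29 of 35 for (a). These counts describe the assumed grid and are not probabilities.

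**Effect on the test.** The ratios give the sign of each participant's difference; the paired t-test averages those differences. A simulation of 10,000 trials with 15 participants assumed s around 0.6 and v around 1.1 (log-scale SD 0.2 and 0.1), a point inside the reversal range. The quotient was significantly higher with the exoskeleton in about 100% of runs. Reading (a) was significantly lower in about 100%, and (b) in 99.9%. This shows that 15 participants can be enough for a significant result in the wrong direction. It does not predict what this trial will find.

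**The case against.** The strongest reply is that this is a drafting slip that no competent analyst would follow. The product of speed and weight is the right denominator, and only the words for division are missing. The neighbouring text drops words too: the sentence on walking with and without the device in items 9B and 10B has lost its verb. The intended construct is clear from the Background and Objectives, and the cited source, which cannot be consulted here, may contain the formula. This is very likely right about intent. It does not cure the text, because the protocol holds the only prespecified definition of a tested outcome and following it gives a wrong result. The repetition in item 10A looks like copied text and says nothing about intent either way.

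Second, reading (a) is strained, since the sentence says the calculation starts from oxygen consumption. That is fair. The case does not need (a); reading (b) is enough.

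Third, the size is hypothetical. That stands: 14 of the 26 reversed cells under (b) come from s = 0.5 and 0.6, and at s = 0.9 only 2 of 7 reverse. Hence the claim is only that the definition can reverse the comparison.

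Fourth, this is a pilot whose raw data would survive, so the quotient could be computed later. That is true, and it makes the correction cheap, but a formula chosen after the data are seen is no longer prespecified.

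Finally, a corrected formula leaves other questions open: whether oxygen consumption over a walk of about 13 seconds (7.62 m at the assumed 36 m/min) can be interpreted, and whether rests in the 6-minute test count towards gait speed. These are separate points and do not weaken this one.

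**Conclusion.** The concern holds and should be corrected before analysis. The printed definition does not measure oxygen used per unit distance, and it conflicts with the plan's own construct and favourable direction. That conclusion needs no assumed values.

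How much it matters depends on how far gait speed differs between conditions, which the documents do not tell us. With equal speeds the direction is unaffected. With a slower walk in the device, reading (b) gives the opposite direction whenever s < v < 1/s; at s = 0.7 and v = 1.2, a 71% higher cost per metre would be reported as a 16% lower score. The finding concerns the rule as written. It does not claim that the team will compute it that way.

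**What to change.** In Outcome Measures items 9A and 10A, replace the defining sentence with:

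> Oxygen cost (mL/kg/m) = oxygen consumption (mL/min) divided by the product of gait speed (m/min) and body weight (kg), with consumption and speed taken over the same time window of the same trial. If the device output is already in mL/kg/min, divide by gait speed only.

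Add which body weight is used (measured when, and that device weight is not included), and that the same value applies with and without the exoskeleton. While editing, state whether resting time in the 6-minute test counts in gait speed.

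The cost is one sentence of wording in two places. Oxygen consumption is already recorded, and speed follows from the timed or measured walks. Body weight is not listed in the schedule of assessments, but it is needed for the eligibility limit under Study Population, so it only has to be kept with the outcome data.

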### Exoskeleton Training

Subjects will participate in individualized training sessions using Ekso®. Each training session will last up to 60 minutes, 5 days per week for 3 weeks, for a total of 15 sessions.

During the training, subjects will wear a lower extremity exoskeleton robotic walking device. Subjects will participate in individualized treatment sessions which may include: sit to stand, static and dynamic standing balance, weight shifting, walking, turning, and stand to sit. Each training session will last up to 90 minutes (60 minutes of training with 30 minutes for setup, don/doff of device) and training will be held 5 days per week for 3 weeks with a total of 15 sessions.

The training intensity and frequency is adapted from our ongoing research protocol for Spinal Cord Injury (SCI) robotic exoskeleton locomotion training (unpublished data, HMSC-13-0536). These SCI participants with paraplegia (either motor incomplete or complete SCI) can stand and walk with assistance devices (walker or canes) prior to the training and are able to walk with exoskeleton with moderate trainer assistance for at least 100 meters on a level surface at the end of 15 training sessions. Therefore we think this training intensity and duration will apply in individuals with MS who can stand and walk with assistance devices. Initial training will be focused on static and dynamic standing balance and weight shift training with EKSO. This will progress to more difficult activities, such as transitioning from sit-to-stand and stand-to-sit, walking, and turning depending on each subject's capability. A trainer will always be present during the training sessions to provide varying levels of assistance. As a subject's skill with the powered exoskeleton improves, the need for trainer assistance will be proportionately reduced. The level of assistance will be quantified by 4 categories of trainer-assisted efforts: (1) maximal assistance – both hands on the pelvic band of the device for significant and frequent weight shift and balance support to the participant; (2) moderate assistance–both hands on the pelvic band or other part of the device for occasional weight shift and/or balance support to the participant; (3) minimal assistance—one hand on the device for infrequent balance support; and (4) close contact guard/no assistance–no hand on the device, but is near enough to be able to provide assistance if necessary [6]. To monitor safety and fatigue, we will ask all subjects periodically during training sessions about their perceived

exertion using Borg Rating of Perceived Exertion Scale (RPES) [7]. Training will be stopped if a subject reports a level of 17 or greater, and will only be resumed after rest.

#### Assessment of participant status after each training session:

Additionally, for every session, participant's physical comfort will be monitored for documentation of safety. Pain, discomfort, fatigue will be assessed at the start and end of each experimental session on a 11-point visual analogue scale ranging from 0 (none) to 10 (worst). Physical and cognitive demand assessment data will be recorded as well. The progress note will also document experimental session details (e.g., task performed, date, time etc.). The data collected through this survey will help monitor safety and comfort of using device on a session-by-session basis throughout the training period.

All collected assessment data forms will be de-identified and only include the coded-name for each participant.

#### Photography and Videotaping:

A portion of the assessment and training sessions will be photographed and videotaped for scientific publications and presentations. Subjects' consent will be required to perform any photography and videotaping. Subject identity will be protected in any published photography and videotaping placing a black square across subject's face.

### **Data and Safety Monitoring**

We will use following strategies to prevent some expected events for this study:

#### 1) Loss of confidentiality or privacy

Information obtained for this study will be kept private to the extent allowed by law. However, research information may be shared with the University of Texas Health Science Center at Houston Institutional Review Board (IRB), the research physician investigator, the research staff and others who are responsible for ensuring compliance with laws and regulations related to research.

The study will be performed at The Institute for Rehabilitation and Research (TIRR) Memorial Hermann in the physical therapy gym. All data collection records will be locked in the Study Coordinator's office in a locked file cabinet. The only data entered electronically will be de-identified data. All computers are password protected and therefore, only authorized persons have the access to the electronic files saved in computers and will adhere to TIRR MEMORIAL HERMANN standards.

#### 2) Loss of saved electronic data after a computer crash

All original data will be maintained on paper data collection forms. De-identified data may be entered into computer for data analysis. A standard procedure of electronic file backup is established and enforced by the PI. All file backups are routinely performed in the local hard drive.

However, if there are other unanticipated problems which occur during and after data collection: the original paper version of the data will be maintained in the locked file cabinet.

